### 4.4. Exploratory Efficacy – DB Period

Exploratory efficacy endpoints in the DB period include:

- change from baseline in all other hormone parameters (adrenocorticotropic hormone [ACTH], total testosterone, follicle stimulating hormone [FSH], luteinizing hormone [LH], progesterone, and sex hormone binding globulin [SHBG]) at Week 24
- change from baseline in urine androgen metabolite levels at Week 24

- change from baseline in metabolic laboratory parameters (total cholesterol, low-density lipoprotein [LDL], high-density lipoprotein [HDL], glycated hemoglobin [HbA1c], triglycerides) at Week 24
- change from baseline in bone mineral density (BMD) at Week 24
- change from baseline in total lean body mass at Week 24
- change from baseline in total body mass (by DXA) at Week 24
- change from baseline in hirsutism (female subjects only) at Week 24
- change from baseline in acne (female subjects only) at Week 24
- change from baseline in bone markers (serum osteocalcin, serum bone-specific alkaline phosphatase, serum C-terminal telopeptide [CTX], urine N-terminal telopeptide [NTx]) at Week 24
- change from baseline in body mass index (BMI) at Week 24
- achievement of a reduction in glucocorticoid dosing regimen instances per day at Week 24 (subjects on a hydrocortisone-alone regimen at baseline)
- achievement of switching to a hydrocortisone-alone glucocorticoid dose regimen at Week 24 (subjects on prednisone [or equivalent] or prednisone [or equivalent] plus hydrocortisone at baseline)
- achievement of switching to a hydrocortisone-alone glucocorticoid dose regimen at Week 24 (subjects on a dexamethasone-containing glucocorticoid regimen at baseline)
- achievement of switching to a dexamethasone-free glucocorticoid dose regimen at Week 24 (subjects on a dexamethasone-containing glucocorticoid regimen at baseline)

#### **4.5. Exploratory Efficacy – OL Period**

Exploratory efficacy endpoints in the OL period include:

- percent change from baseline and OL baseline in glucocorticoid daily dose (in hydrocortisone equivalents adjusted for BSA [mg/m^2/day]) at Month 12, while Month 12 androstenedione values are adequately controlled at  $\leq 120\%$  of baseline or  $\leq$  ULN for age and sex
- achievement of a reduction in glucocorticoid daily dose to physiologic levels at Month 12
- change from baseline and OL baseline in hormone parameters (androstenedione, 17-OHP, ACTH, total testosterone, FSH, LH, progesterone, SHBG) at Month 12
- change from baseline and OL baseline in metabolic laboratory parameters (glucose tolerance [as measured by the post-GTT load glucose levels; in subjects without diabetes mellitus], HOMA-IR [in fasting subjects not on insulin], total cholesterol, LDL, HDL, HbA1c, triglyceride) at Month 12
- change and percent change from baseline and OL baseline in weight at Month 12
- change from baseline and OL baseline in BMI at Month 12

- change from baseline and OL baseline in waist circumference at Month 12
- change from baseline and OL baseline in percent total fat mass at Month 12
- change from baseline and OL baseline in total lean mass at Month 12
- change from baseline and OL baseline in total body mass (via DXA) at Month 12
- change from baseline and OL baseline in urine androgen metabolite levels at Month 12
- change from baseline and OL baseline in BMD at Month 12
- change from baseline and OL baseline in hirsutism (female subjects only) at Month 12
- change from baseline and OL baseline in acne (female subjects only) at Month 12
- change from baseline and OL baseline in bone markers (serum osteocalcin, serum bone-specific alkaline phosphatase, serum C-terminal telopeptide [CTX], urine N-terminal telopeptide [NTx]) at Month 12
- change from baseline and OL baseline in testicular adrenal rest tumor (TART) volume (expressed as a percentage of the total testicular volume) at Month 12 (male subjects only)
- change from baseline in menstrual regularity (premenopausal female subjects not using hormonal or IUD contraception only) at Month 12
- change in number of menstrual periods (premenopausal female subjects assigned to the placebo group for the DB period, not using hormonal or IUD contraception) at Week 24 to Month 12, compared to Day 1 to Week 24

## 4.6. Safety

Safety endpoints in the DB and OL periods include:

- Occurrence of treatment-emergent adverse events (TEAEs), treatment-emergent serious adverse events (TESAEs), adrenal insufficiency TEAEs, and TEAEs leading to discontinuation from study
- Observed and changes from baseline in clinical laboratory test values (including hematology, clinical chemistry, plasma renin activity [PRA], and coagulation)
- Observed and changes from baseline in vital sign values
- Observed and changes from baseline in 12-lead electrocardiogram (ECG) intervals
- Observed and changes from baseline in total scores from the Brief Psychiatric Rating Scale (BPRS)
- “Yes” responses to suicidal behavior or ideation at postbaseline assessments from the Columbia-Suicide Severity Rating Scale (C-SSRS)

## 4.7. Pharmacokinetics

The pharmacokinetic endpoint is observed plasma concentrations of crinecerfont and its metabolites

## **4.8. Patient-Reported Outcomes**

PRO endpoints in the DB and OL periods include:

- Observed and change from baseline values for the 8 health concepts and the 2 summary measures from the 36-Item Short Form Health Survey (SF-36)
- The 5 levels for each health dimension from the EQ-5D-5L over time
- Observed and changes from baseline in global fatigue index (GFI) values from the Multidimensional Assessment of Fatigue (MAF)
- Observed and changes from baseline in total score values from the Psychological General Well-Being Index (PGWBI)
- Observed and changes from baseline values in the quantity of sleep and the two problem indices from the Medical Outcomes Study 12-Item Sleep Scale (MOS-12)

## 5. DATA ANALYSES

### 5.1. Interim Analysis

An unblinded interim analysis on the primary endpoint using the “promising zone” method ([Mehta and Pocock, 2011](#)) will be conducted when approximately the first 76 subjects (approximately 46% of the planned number of enrolled subjects) have had the opportunity to complete the Week 24 assessments. The promising zone method as planned in this study was shown to not inflate the type I error, as described in the simulation report attached to the Adaptation Plan. This interim analysis, in conjunction with the final analysis method described in Section 9.3.2, will not require an adjustment to the level of significance for the final analysis of the Week 24 data. The interim analysis will be conducted by an ISC and will be evaluated by the DMC. The DMC will assess futility and consider sample size re-estimation based on the observed treatment effect and the conditional power at the time of the interim analysis.

Conditional power (CP) is the probability that, conditional on the current value of the test statistic at the interim analysis, the study will achieve statistical significance at the final analysis.

At the time of the interim analysis, the CP will be calculated and the following actions will be recommended, based on the interim observed treatment effect ( $\delta_{int}$ ) which is the difference in mean percent change in the primary endpoint between the crinecerfont and placebo treatment groups, and the interim CP calculation:

$\delta_{int} < 0.05$	Futility Zone. Recommend stopping for futility
$CP < CP_{min}$	Unfavorable Zone. Continue to the planned sample size as the results are currently ‘unfavorable’
$CP_{min} \leq CP < CP_{max}$	Promising Zone. The results are currently in the ‘promising zone’. Increase the sample size, up to a maximum of 210 subjects, to achieve a conditional power of $CP_{max}$
$CP \geq CP_{max}$	Favorable Zone. Continue to the planned sample size as the results are currently ‘favorable’

The adaptive elements of this interim analysis and the criterion for each DMC recommendation are detailed in an Adaptation Plan. The Adaptation Plan describes the values of  $CP_{min}$ ,  $CP_{max}$ , and the values of CP that result in different sample size increases. In order to maintain study integrity, access to the Adaptation Plan will be limited to the ISC, DMC, and selected Sponsor staff assigned to the crinecerfont program, specifically the biostatisticians, regulatory lead, and program team lead.

Subjects assessed for the primary efficacy endpoint prior to the time of the interim analysis comprise the Stage 1 sample, and those subjects assessed after the interim analysis comprise the Stage 2 sample. Based on the Stage 1 and Stage 2 subject samples, the two independent stage-wise test statistics for superiority,  $Z_1$  and  $Z_2$ , will be computed as follows:

**Stage 1 test statistic:** The Stage 1 test statistic is given by:

$$Z_1 = \hat{\delta}_1 / se(\hat{\delta}_1)$$

calculated from an ANCOVA model adjusting for the randomization stratification factors and relevant baseline value as a covariate, using subject data from Stage 1. Here,  $\hat{\delta}_1$  denotes the estimate of  $\delta$  based on Stage 1 data, and  $se(\hat{\delta}_1)$  denotes its standard error.

**Stage 2 test statistic:** Similarly, the Stage 2 test statistic is defined by

$Z_2 = \hat{\delta}_2 / se(\hat{\delta}_2)$ , calculated from an ANCOVA model adjusting for the randomization stratification factors and relevant baseline value as a covariate using subject data from Stage 2. Here,  $\hat{\delta}_2$  denotes the estimate of  $\delta$  based on Stage 2 data, and  $se(\hat{\delta}_2)$  denotes its standard error.

With the conventions outlined above, CP at the interim analysis will be calculated as follows:

$$CP_{\hat{\delta}} = P_{\hat{\delta}} \left( Z_2 \geq \frac{c_2 - \sqrt{w} Z_1}{\sqrt{1-w}} \middle| Z_1 \right) = 1 - \Phi \left( \frac{c_2}{\sqrt{1-w}} - \frac{\sqrt{1-w}}{\sqrt{w}} Z_1 - \frac{\sqrt{w}}{\sqrt{1-w}} Z_1 \right)$$

where  $w$  is the information fraction at the time of the interim analysis based on the planned number of 165 subjects, and  $c_2 = \Phi^{-1}(0.025) = 1.96$  is the efficacy boundary at final analysis with  $\Phi$  being the cumulative distribution function of the standard normal distribution.

Based on the interim analysis results, one of the following three recommendations will be made by the DMC:

- Stop the study for futility
- Continue the study to the planned sample size
- Increase the sample size, up to a maximum of 210 subjects

The DMC will communicate the recommendation, without disclosing the numerical results, to a designated group of Sponsor personnel (Sponsor Review Committee [SRC]), who are not involved in the crinecerfont program. The SRC members will be firewalled from the crinecerfont study team and will keep the results confidential until the final analysis of the Week 24 data. The membership, responsibilities, and logistical considerations of the SRC are detailed in the SRC Charter.

Details about the final analysis of the primary endpoint, adjusting for the interim analysis, are outlined in Section 9.3.2.

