## 6.6. Derived and Transformed Data

Change from baseline is calculated as the postbaseline value minus the baseline value; a negative value will represent a decrease at the postbaseline visit. Percent change from baseline is calculated as:  $\text{change from baseline}/\text{baseline value} \times 100$ . If either the baseline or postbaseline value is missing, the change from baseline and/or percent change from baseline will also be missing. The percent change from baseline will also be missing if the baseline value is equal to 0.

With the exception of pharmacokinetic concentration data, all below the lower limit of quantification (BLQ) values will be set equal to the BLQ value in all summaries. For values that are above the upper limit of quantification (ULQ), the value will be set equal to the ULQ.

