The primary analysis of the primary endpoint will be performed using the CHW test statistic (Cui, Hung, Wang, 1999) comprising test statistics from stage 1 of the trial (the interim dataset), and stage 2 of the trial (the remaining part of the trial). Each test statistic will be generated using an analysis of covariance (ANCOVA) model, as described in Section 9.2.1. If the total sample size was increased in a data-dependent manner as a result of the interim analysis, the primary analysis of the primary endpoint will be performed using the CHW test statistic, as proposed by Cui, Hung, and Wang (1999) and independently by Lehmacher and Wassmer (1999), to determine statistical significance. The CHW test statistic is a weighted test statistic comprised of test statistics from stage 1 of the trial (the interim dataset) and stage 2 of the trial (the remaining part of the trial). Each test statistic will be generated using an ANCOVA model, as described in Section 9.2.1. The independent increments of the Z statistics (i.e., the Wald statistics constructed using model-based treatment effect estimates) of the 2 stages are combined by pre-specified weights that are based on the planned proportion of total number of subjects at which the interim analysis would be taken if there were no change in the design.

In the present case, the study is designed for 165 subjects with an interim analysis after approximately 76 subjects are evaluated for the primary efficacy endpoint. Therefore, the planned proportions are 0.46 and 0.54 for the two stages, respectively. The independent incremental Z statistics for the 2 stages are combined with weights that equal the square root of 0.46 for Stage 1 and square root of 0.54 for Stage 2. Hypothesis test of the null hypothesis  $H_0: \delta \leq 0$ , tested at one-sided 2.5% level at final analysis, is based on the CHW test statistic,  $Z_{CHW}$ , which combines the independent stage-wise test statistics defined in Section 5.1, as follows:

$$Z_{CHW} = \sqrt{w} Z_1 + \sqrt{1-w} Z_2.$$

The p-value is defined by  $P_{CHW} = \Phi(Z_{CHW})$ , where  $\Phi$  is the cumulative probability based on standard normal distribution. Gao et al (2008) have shown that the type-1 error is preserved at the specified  $\alpha$  level despite the possibility of a data-dependent increase in the sample size.

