If the total sample size is not increased in a data-dependent manner as a result of the interim analysis, the primary analysis of the primary endpoint will be performed using the conventional test statistic generated from an ANCOVA model (as described in Section 9.2.1) to determine if statistical significance is reached. As a sensitivity analysis, the CHW test statistic will be computed as described above.

All sensitivity and supplementary analyses outlined in Sections 9.3.3 and 9.3.4 will use the same method (ie, CHW test statistic or conventional test statistic) as the primary analysis of the primary endpoint.

Statistical significance for the treatment comparison will be determined using the multiple comparison procedure described in Section 9.1. Descriptive statistics and LS means for the percent change from baseline in total glucocorticoid daily dose (with androstenedione control) at Week 24 will be presented by treatment group along with the LS-mean treatment difference, 95% confidence intervals, and p-value.

Descriptive statistics will be presented by treatment group for the glucocorticoid total daily dose ( $\text{mg}/\text{m}^2/\text{day}$ ) observed, change from baseline, and percent change from baseline values at baseline (observed data) and each postbaseline visit. Mean ( $\pm \text{SEM}$ ) values of the glucocorticoid total daily dose at each visit will be summarized in line graphs by treatment group. Similar graphs will be presented for the change from baseline and percent change from baseline. These summaries will be presented for both the glucocorticoid total daily doses *without* the derivation of 0 for loss of androstenedione control as well as the glucocorticoid total daily doses *with* the derivation of 0 for loss of androstenedione control (for change from baseline and percent change from baseline summaries only).

The analyses described in this section for the primary efficacy endpoint will be repeated for the full analysis set excluding site number 1083.

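### SAP 9.3.2 prints the CHW p-value in the wrong tail for its own null hypothesis; the direction of delta, the c2 expression and the futility unit need clarifying alongside it

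*SAP*

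**What the plan says.** SAP 6.6 calculates percent change on a ×100 scale, and "a negative value will represent a decrease at the postbaseline visit". A reduction in glucocorticoid dose, which is the benefit sought, is therefore negative for each subject.

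SAP 5.1 introduces the interim treatment effect, "which is the difference in mean percent change in the primary endpoint between the crinecerfont and placebo treatment groups". It does not say which mean is subtracted from which. Protocol 13.3 names the two group means but forms no difference. The futility zone is "\delta_{int} < 0.05", without a unit. Section 5.1 then defines Z1 and Z2 as "the two independent stage-wise test statistics for superiority", calculates conditional power as the chance that Z2 exceeds an upper threshold, and gives the final boundary as "c_2 = \Phi^{-1}(0.025) = 1.96", with Φ the standard normal distribution function. It adds: "The adaptive elements of this interim analysis and the criterion for each DMC recommendation are detailed in an Adaptation Plan".

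SAP 9.3.2 states H0: δ ≤ 0 at one-sided 2.5%, combines the stages with weights √0.46 and √0.54, and defines the p-value as P_CHW = Φ(Z_CHW), where Φ "is the cumulative probability based on standard normal distribution". This test decides the primary endpoint if the sample size was increased after the interim. If it was not, the conventional ANCOVA statistic decides, and "As a sensitivity analysis, the CHW test statistic will be computed as described above".

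**The concern.** With H0: δ ≤ 0, evidence for the drug is a large positive Z, and the one-sided p-value is the area above it. The printed formula takes the area below. Followed literally after a sample-size increase, it would put a p-value near 1 beside a clearly favourable estimate on the primary endpoint. Under SAP 9.3.2 the sensitivity and supplementary analyses of that endpoint use the same method as the primary analysis, so they would inherit the error. Under SAP 9.1, testing of the key secondary endpoints depends on the primary result.

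Three smaller gaps lie in the same method. The direction of δ can be inferred but is not stated. The expression for c2 does not equal the value printed beside it. The futility cutoff can be read on two scales that differ by a factor of 100.

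**Working it through.** **Figures that reproduce.** For 110:55 at effect size 0.55 (SAP 3.3), power is 91.5% by the normal approximation and 91.2% by the t-test, in line with the stated figure above 90%. 76/165 = 0.461 matches the weight 0.46. The two forms of the conditional power formula agree (Z1 = 1.5 gives 0.634 in both).

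**Does either direction of δ reconcile the formulas?**
- Placebo minus crinecerfont (benefit positive): the futility rule, the upper-tail conditional power, the boundary +1.96 and H0: δ ≤ 0 all fit. Φ(Z_CHW) does not.
- Crinecerfont minus placebo (benefit negative): Φ(Z_CHW) fits, but H0 and conditional power point the wrong way. At effect size 0.55, a working drug would fall in the futility zone at about 98.8% of interims (51:25 split).

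Neither direction works throughout. The first needs one formula changed; the second needs nearly all of them changed.

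**Size of the tail error.** At the boundary, Φ(1.96) = 0.975 and 1 − Φ(1.96) = 0.025.

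For the branch where the formula decides, the inputs are effect size 0.55, 2:1 allocation, 76 subjects in stage 1 and a maximum of 210 in total. CPmin = 0.30 and CPmax = 0.95 are assumed, because the documents do not give them.
1. The SAP conditional power formula (w = 0.46, c2 = 1.96) gives CP = 0.30 at Z1 = 1.07 and CP = 0.95 at Z1 = 2.15.
2. With 2:1 allocation the expected stage-wise Z is d√(2n/9). For 134 stage 2 subjects this is 0.55 × √(268/9) = 3.00.
3. Lower end, N = 210: Z_CHW = 0.678 × 1.07 + 0.735 × 3.00 = 2.93. Printed p = 0.998; correct p = 0.0017.
4. Upper end. SAP 5.1 raises N only far enough to reach CPmax. With n2 subjects in stage 2, conditional power is 1 − Φ[(1.96 − 0.678 Z1)/0.735 − Z1√(n2/76)]. At n2 = 134 this equals 0.95 when Z1 = 1.92. Above that, N falls: Z1 = 2.00 needs about N = 192 (expected Z_CHW 3.41), and Z1 = 2.14 about N = 167 (3.27).
5. The maximum is therefore near Z1 = 1.92: 0.678 × 1.92 + 0.735 × 3.00 ≈ 3.5. Printed p ≈ 0.9998; correct p ≈ 0.0002.

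**c2.** Φ⁻¹(0.025) = −1.96 and Φ⁻¹(0.975) = +1.96. The printed value is right; the expression is not.

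**Futility cutoff.** At n = 76, SE = SD × √(1/50.67 + 1/25.33) = 0.243 × SD. The documents give no SD, so 15 to 40 points is assumed (SE 3.65 to 9.73). The chance of landing in the futility zone is Φ[(cutoff − effect)/SE].

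| Reading of 0.05 | No effect | Effect size 0.55 |
|---|---|---|
| 0.05 point | about 50% | about 1% |
| 5 points, SD 15 | Φ(5/3.65) = 91% | Φ((5 − 8.25)/3.65) = 19% |
| 5 points, SD 20 | 85% | 11% |
| 5 points, SD 40 | Φ(5/9.73) = 70% | Φ((5 − 22)/9.73) = 4% |

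**The case against.** The strongest reply is that the plan already contains a usable decision rule. SAP 5.1 prints 1.96 as the efficacy boundary for superiority statistics, and 9.3.2 fixes one-sided 2.5%. Comparing Z_CHW with 1.96 settles significance without the p-value line. SAP 9.3.2 also reports the estimate and 95% confidence interval with the p-value, so 0.998 beside a favourable estimate would be noticed, and SAP 14 provides for program verification and output review. This stands, and it limits the consequence. It does not make the formula right: a programmer would have to depart from the written specification to get the correct answer.

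The error also reaches the primary test only if the sample size is increased. That stands too.

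A term lost when the PDF was read as text cannot be fully excluded, although the 1 − Φ in the conditional power formula survived. It is easily checked in the source, and it would not supply the order of subtraction or the cutoff's unit.

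The Adaptation Plan, which is not among the documents, may define the direction and the unit for the interim. The final p-value, however, is specified in SAP 9.3.2.

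**Conclusion.** The CHW p-value is wrong as written. It contradicts H0 in the same section and the conditional power formula and 1.96 boundary in SAP 5.1. The value 0.975 instead of 0.025 at the boundary needs no assumption. The range of about 0.998 to 0.9998 instead of about 0.0017 to 0.0002 rests on effect size 0.55 and the assumed conditional power limits. Without a sample-size increase, only the CHW sensitivity analysis is affected.

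Some stronger conclusions that a reader might draw are not supported:
- That a positive trial would be declared negative, or that type I error or the design is compromised. The printed 1.96 gives the correct decision.
- That conditional power would be calculated with −1.96. The value 1.96 is printed, so the c2 slip has no operational effect.
- That the direction of δ is open. Three elements of the plan imply placebo minus crinecerfont; it only needs stating.
- That the futility rule is mis-set, or that 5 points was intended. The SAP does not show this, the DMC criteria are in the Adaptation Plan, and the stopping rates above depend on an assumed SD, with the worst of them at SD 15. The supportable point is that the unit is missing.

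**What to change.** In SAP 9.3.2, write P_CHW = 1 − Φ(Z_CHW), compared with one-sided 0.025. Report 2[1 − Φ(|Z_CHW|)] as the two-sided p-value for use with the 0.05 level in SAP 9.1. Define δ once, as mean percent change on placebo minus mean percent change on crinecerfont, so that benefit is positive in both 5.1 and 9.3.2.

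As accompanying clarifications in SAP 5.1, write c2 = Φ⁻¹(0.975) = 1.96, and state the unit of the futility cutoff on the Section 6.6 ×100 scale, reconciled with the Adaptation Plan.

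The cost is four text or formula corrections, plus a check of the cutoff by someone with access to the Adaptation Plan. No new data and no design change are needed.
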